Norepinephrine reuptake inhibitors are a class of medications that are likely to be effective at facilitating smoking cessation but are currently understudied. Nortriptyline has been shown to be effective at increasing quit rates in several placebo controlled studies and is thought to work via inhibition of norepinephrine reuptake.² Despite its efficacy, nortriptyline use is limited due to its other pharmacological properties (e.g. blockade of muscarinic and histamine receptors) which are responsible for side effects such as dry mouth, constipation, drowsiness and in overdose situations delayed cardiac conduction. Due to its adverse effect profile and lack of FDA indication for smoking cessation, nortriptyline is not currently recommended as a first line therapy for smoking cessation.¹ None of the other approved medications act primarily via norepinephrine reuptake inhibition. Therefore, in order to confirm that norepinephrine reuptake inhibition is an important mechanism by which smoking cessation can be facilitated, studies are needed with other norepinephrine reuptake inhibitors that are well tolerated. Levomilnacipran (recently approved for treating major depressive disorder) fits these criteria but there is no data regarding its effect on smoking.

The proposed pilot study will use novel, recently published methods to assess if levomilnacipran is likely to be effective at increasing smoking cessation rates. This rapid assessment study design developed by Perkins et al allows for the efficacy of a smoking cessation medication to be assessed more quickly and at lower cost than if a full scale clinical study were to be conducted.³⁻⁶ Positive results would lead to studies that could more definitively assess the efficacy of this agent at increasing smoking cessation rates. Conversely, negative results would suggest that norepinephrine reuptake inhibition is not an important mechanism by which medications can increase quit rates and that other mechanisms need to be explored.

2 Objectives

Specific Aim and Hypothesis

The central hypothesis of this project is that norepinephrine reuptake inhibitors in general and levomilnacipran in particular are effective at increasing smoking cessation rates.

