In a series of three papers, this method was used to test four medications. Three of the medications tested are known to increase smoking cessation rates (i.e. nicotine patch, bupropion, varenicline) and one medication tested is known to not increase smoking cessation rates (i.e. modafanil). Number of days abstinent (the primary outcome) was significantly higher during use of all three effective medications relative to placebo thereby demonstrating this method's sensitivity.⁴⁻⁶ The number of days abstinent was not different between modafanil and placebo thereby demonstrating this method's specificity.⁵ By examining motivation to quit on outcomes, the developers of this method found that the best results were obtained when those interested in cessation were recruited for studies using these methods.

In order to determine if levomilnacipran is potentially effective at increasing smoking cessation rates, we will use the medication testing methods described and validated by Perkins et al.³

b) Study Design Overview: We will utilize a cross-over, double-blind study design. Three weeks of the study will be to evaluate levomilnacipran and three weeks will be to evaluate placebo with the two evaluation periods occurring in random order (i.e. one-half of the subjects will receive levomilnacipran followed by placebo, whereas the other half will first receive placebo followed by levomilnacipran). The first week of each three week evaluation period will be to obtain baseline values, the second week to titrate medication and the third week to evaluate efficacy. In order to determine if effects of levomilnacipran depend on the type of cigarettes smoked (i.e. menthol vs. non-menthol), we will enroll an equal number of those smoking each type of cigarette.

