a.4) Data analysis: A paired t-test will be used to test treatment effect based on days of abstinence per quit assessment week (range 0-5, not necessarily consecutive) between levomilnacipran and placebo. Additional separate analyses for menthol and non-menthol cigarette smokers will be conducted. A two-sample t-test will be used to compare the difference in days of abstinence per quit assessment week for menthol cigarette smokers compared to non-menthol cigarette smokers.

Repeated measures Analysis of Variance (ANOVA) will be used for days of abstinence per quit assessment week, assuming mixed effects three-factor ANOVA model (“Order of phases” with two levels, “Treatment” with two levels, “Menthol cigarettes smoker” with two levels, subject effects are random); then use contrasts to compare treatment with placebo for all participants and for menthol cigarette smokers and non-menthol cigarette smokers separately. This approach allows us to investigate primary and secondary aims simultaneously, therefore, to potentially achieve higher statistical power. The use of paired t-tests, on the other hand, provides a proper tool for sample size determination as seen in the following section.

Generalized estimating equation (GEE) model will be used to analyze the longitudinal data, with the number of subjects able to maintain continuous abstinence on all 5 days throughout the quit week as the secondary outcome. Treatment effect (levomilnacipran vs. placebo) and cigarette type effect (menthol vs. non-menthol) will be estimated.

Secondary variables such as scores on the MNWS, SSS and QSU-Brief will be summarized by the mean, standard deviation, median and range. The change in these measures occurring between baseline (i.e. the first week of treatment) and the last day of the third week will be compared between drug and placebo. Similar two-factor ANOVAs will be used to analyze each of the calculated differences as the primary endpoint. Additionally, frequency of subject reported adverse events will be compared between treatments via the use of paired t-tests.

a.5) Power Consideration: The adequacy of planned sample sizes are assessed using two-sided paired t-test. We tested the “minimum detectable difference”, expressed as the number of standard deviations (i.e. “effect size”) for several sample sizes where the two-sided paired t-test is pre-set at a 5% significance level and 80% power. The variability is based on estimates found

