in the literature by others using these methods.⁵ With a total of 52 subjects completing the study (26 menthol smokers and 26 non-menthol smokers), we are able to detect an effect size of 0.57 standard deviations for the comparisons between levomilnacipran and placebo which is considerably smaller than the effect size of approximately 1.65 reported by Perkins et al for bupropion.⁵ Since we anticipate a 20% attrition rate, we are planning on enrolling 64 smokers in total (32 smokers of menthol cigarettes and 32 smokers of non-menthol cigarettes).

7 Data and Safety Monitoring Plan (DSMP)

The principal investigator in conjunction with the study physician will be responsible for monitoring adverse effects. At the conclusion of each visit subjects will be asked whether they have had any side effects. Any positive response will be followed up with questions regarding details of what the adverse effect was and the severity. To the extent possible, each adverse event will be evaluated to determine 1) its severity (mild, moderate, severe), 2) its relationship to the study medication; 3) its duration and 4) whether it constitutes a serious adverse event.

The participation of any subject will be discontinues if they develop a side effects of greater than moderate severity (as determined by the investigators) or develops any symptoms that in the opinion of the investigators would warrant discontinuation from the study. Participation in the study would also be discontinued if during the course of the study the subject develops a significant medical condition (regardless of whether it can be attributed to the study drug) or is initiated on medication that can be expected to interact with the measures being assessed or increase the risk of being on the study medication. The subject has the option of discontinuing their participation at any time for any reason. Adverse events will be reported to the IRB as required per IRB guidelines.

8 References

1. Fiore MC, et al. *Treating tobacco use and dependence: 2008 Update. Clinical Practice Guidelines. U.S. Department of Health and Human Services. Public Health Service*. Rockville, MD2008.
2. Hughes JR, et al. Antidepressants for smoking cessation. *Cochrane Database Syst Rev*. 2014;1:CD000031.
3. Perkins KA, et al. An efficient early phase 2 procedure to screen medications for efficacy in smoking cessation. *Psychopharmacology (Berl)*. 2014;231:1.

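### The only planned comparison of adverse events is a paired t-test, which cannot use subjects stopped in their first period; a table by treatment received would include them (minor)

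*Combined protocol and SAP*

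**What the plan says.** Section 6 a.2 lists the frequency of reported adverse events among the other outcomes. Section 6 a.4 gives the analysis in one sentence: "frequency of subject reported adverse events will be compared between treatments via the use of paired t-tests". The mixed-effects ANOVA and GEE models in a.4 are assigned to the abstinence outcomes, and the two-factor ANOVAs to the withdrawal, mood and craving scales. None is assigned to adverse events.

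Section 7 sets the stopping rule: "The participation of any subject will be discontinues if they develop a side effects of greater than moderate severity". It also describes collection: "At the conclusion of each visit subjects will be asked whether they have had any side effects", and "each adverse event will be evaluated to determine 1) its severity (mild, moderate, severe), 2) its relationship to the study medication; 3) its duration".

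Section 4 b) fixes the order of treatment: "one-half of the subjects will receive levomilnacipran followed by placebo, whereas the other half will first receive placebo followed by levomilnacipran". Section 6 a.5 allows for loss: "Since we anticipate a 20% attrition rate, we are planning on enrolling 64 smokers in total", with the power calculation based on 52 completers.

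The plan does not define a safety population, a table of events by treatment received, a comparison of withdrawals for adverse events, or the handling of a subject with only one treated period.

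**The concern.** The rule that removes a subject is triggered by the outcome being compared, and it acts on the worst events. A levomilnacipran-first subject stopped in period 1 has no placebo value, so no difference can be formed. A placebo-first subject stopped on levomilnacipran in period 2 does form a difference, provided a shortened period is accepted.

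At stake is what the pilot can report about tolerability. Section 1 gives tolerability as part of the reason for testing this drug: "studies are needed with other norepinephrine reuptake inhibitors that are well tolerated". Events severe enough to stop a subject are the most direct evidence against that premise, and the stated comparison is least able to show them.

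**Working it through.** **The plan's own figures.** The documents give no figure for the adverse-event comparison. The nearest is the attrition allowance. 64 × 0.80 = 51.2, close to the 52 completers; the exact inflation is 52/0.80 = 65. So 64 − 52 = 12 subjects may be lost, with no breakdown by cause, treatment or period.

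**Inputs.** From the documents: 64 enrolled, hence 32 per order under 1:1 allocation; withdrawal for a side effect worse than moderate. Assumed, because the documents give no rates: stopping risk per exposure qL on levomilnacipran and qP on placebo, the same in both periods, independent within subject, and no other dropout.

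**Step 1: share of levomilnacipran stops with no pair.** Stops in period 1 number 32·qL. Stops in period 2 number 32·(1 − qP)·qL. The unpaired share is

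32·qL / [32·qL + 32·qL·(1 − qP)] = 1/(2 − qP),

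which does not depend on qL. For qP = 1%, 2% and 3% it is 50.3%, 50.5% and 50.8%. If a fraction r of placebo-first subjects is lost for any reason before their levomilnacipran period, the share is 1/(2 − r). At r = 20%, the whole attrition allowance, this is 55.6%. With within-subject correlation of 0.6 at 10% vs 2%, simulation gives 53%.

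The expected number of levomilnacipran subjects without a pair is 32·qL: 1.6, 3.2 and 4.8 at qL = 5%, 10% and 15%.

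**Step 2: what the pairs show, if a shortened period 2 counts.** Pairs number 32(1 − qP) + 32(1 − qL). The difference in the proportion with a stopping event is

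[32·qL(1 − qP) − 32·qP(1 − qL)] / [32(1 − qP) + 32(1 − qL)] = (qL − qP)/(2 − qL − qP).

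| Assumed risk, drug vs placebo | True difference | In the pairs | Share shown | Loss in mean events per subject |
|---|---|---|---|---|
| 5% vs 1% | 4.0 points | 0.04/1.94 = 2.1 points | 52% | 0.04 − 0.021 = 0.02 |
| 10% vs 2% | 8.0 points | 0.08/1.88 = 4.3 points | 53% | 0.08 − 0.043 = 0.04 |
| 15% vs 3% | 12.0 points | 0.12/1.82 = 6.6 points | 55% | 0.12 − 0.066 = 0.05 |

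The last column counts one stopping event per stopped subject. Other events in the lost subjects are not counted.

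**Step 3: completers only.** A subject stopped for an adverse event is by definition not a completer. No stopping event on either treatment enters, and the difference in such events is zero by construction.

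**Step 4: all subjects dosed, by treatment received.** Under the same assumptions this recovers qL − qP: 4.0, 8.0 and 12.0 points. If every subject at risk on placebo is also at risk on drug, it gives 4.0, 8.0 and 12.1. At 10% vs 2% the expected denominators are 32 + 32 × 0.98 = 63.4 on levomilnacipran and 32 + 32 × 0.90 = 60.8 on placebo.

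**The case against.** The plan compares the frequency of all reported events, not of stopping events. On that scale the loss is a few hundredths of an event per subject. The rates are assumed. Even at those rates the shortfall of 1.9, 3.7 or 5.4 points is smaller than the 95% half-width of the paired difference (Wald, about 58 to 62 pairs): 4.3, 6.2 and 7.7 points. Section 5 describes the drug as generally well tolerated and the dose as the lowest recommended for depression. There is no safety hypothesis in a.3, and nothing in a.4 forbids tabulating events.

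All of this stands as an argument about weight. It does not answer the structural point: the one comparison stated excludes subjects because of the outcome being compared, and no other analysis brings them back.

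A reader might infer three stronger things, and the documents support none of them:

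- *That these events go unrecorded.* Section 7 has them asked about at every visit, graded, and reported to the IRB as required. Only a comparison that includes them is missing.
- *That harm is necessarily understated.* Placebo-first subjects stopped in period 1 are lost in the same way. The comparison understates harm only if stopping events are commoner on levomilnacipran.
- *That half of all adverse events are lost.* The half refers to events that stop a subject, and only on the reading that a cut-short period 2 forms a pair.

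**Conclusion.** The point holds as a minor, inexpensive improvement. The stated comparison leaves out about half of the events that stop a subject on levomilnacipran if a shortened second period counts as a pair, and all of them if only completers are analysed. The plan does not choose between these. The half rests on 1:1 order and equal risk in each period. The sizes (4.0 to 12.0 points shown as 2.1 to 6.6) rest on assumed rates as well, and the number of subjects concerned is small and unknown.

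It would be tempting to conclude that the pilot's decision is compromised. It is not: sections 1 and 3 tie further studies to findings on efficacy, so the go decision does not depend on this comparison.

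**What to change.** In section 6 a.4, add:

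> The number and percentage of subjects with at least one adverse event, by type and worst severity, and the number discontinued for an adverse event, will be tabulated by treatment received among all subjects who took at least one dose of that treatment, counting events from first dose in that period and including subjects discontinued in either period. This is the main safety display, and the difference between treatments will be described from it. The paired t-test is supplementary and will be labelled as excluding subjects with only one treated period.

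If an interval for a paired difference in proportions is wanted as well, such as a Tango score interval, label it as limited to subjects dosed in both periods and therefore attenuated; it repeats the exclusion described here.

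The cost is SAP wording and a few descriptive tables from data already collected; no new visit or contact is needed. The estimates will be imprecise, and the two columns will not hold exactly the same subjects.

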c.1) Screening visit: Initial eligibility will be assessed via a phone interview. Those likely to qualify will be scheduled for a screening visit at which written informed consent will be obtained and eligibility confirmed. Psychiatric exclusion will be based on the Primary Care Evaluation of Mental Disorders (PRIME-MD) instrument. The PRIME-MD, designed to be administered by non mental health professionals, has been found to have good agreement with assessments made independently by mental health professionals.¹³ Medical history will be obtained via subject report and a physical exam will be performed to ensure that subjects are in generally good health. A urine pregnancy test will be given to females to confirm that they are not pregnant. Following the screening visit, those subjects who qualify will be scheduled for the remainder of their visits.

c.2) Experimental Protocol: Subjects will participate in two evaluation periods each lasting three weeks. During one of the evaluation periods levomilnacipran will be evaluated whereas during the other evaluation period, placebo will be evaluated. Procedures for the two evaluation periods will be identical, with the order of which period occurs first (i.e. medication or placebo) assigned randomly. The procedures at each study visit are based on published methods. The first week of each period will consist of baseline smoking assessment. This week will also serve as a medication washout period when occurring as the first week of the second three week assessment period (with a terminal half-life of approximately 12 hours,¹¹ this should be a sufficiently long washout period). During this week subjects will be seen at the research clinic twice. At the second baseline week visit subjects will receive their initial supply of medication. Levomilnacipran will be dosed at 20 mg once daily for two days followed by 40 mg once daily for 10 days. This is consistent with the recommended dose for the treatment of depression.

During the second week of the evaluation period, subjects will begin to take their assigned medication (i.e. levomilnacipran or placebo) and will be seen at two visits. At the first of these visits, subjects will receive a supply of the 40 mg dose of medication (or placebo). Adverse events and subjective measures such as craving and withdrawal symptom severity will be assessed at each visit.

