During the third week of the evaluation period, subjects will attempt to abstain from smoking for a five day period and will be seen daily to determine smoking status. These visits will occur on five consecutive days with the visits in most instances occurring Monday through Friday. Subjects will be told to smoke normally until the evening prior to the first of the abstinence assessment days and then to attempt to not smoke at all during the subsequent five days. At each visit, smoking status will be evaluated by measuring exhaled carbon monoxide (CO) concentrations with a value of < 5 ppm confirming abstinence. Each visit during this week will be scheduled in the afternoon in order to assess mid-day CO rather than CO after just waking up. Subject will stop taking medication after they complete their five consecutive days of study visits.

The same procedures will then be repeated except that subjects will receive the alternate treatment. Since continued participation in the study will require subjects to resume smoking, subjects will be told that it is not necessary for them to resume smoking if they wish to remain abstinent; however they would not be able to continue participation in the study if this were the case. At the conclusion of the study, subjects will be given information about resources in the community that could assist them with the smoking cessation attempt. They will additionally be called by telephone approximately 1 week after completing the study in order to ensure that there are no adverse events and to ascertain if they have attempted to quit smoking. Those that have not made a cessation attempt will be encouraged to do so and will again be provided with information regarding community resources to assist them.

Subjects will therefore be seen at a screening visit and at 9 visits per study period for a total of 19 visits.

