e) Outcome Measures: The primary outcome measure is the number of days of confirmed abstinence during the third week of each assessment period (out of a maximum of 5 days). A secondary outcome is the percentage of subjects who are abstinent at all five cessation visits.

Additionally at each visit, subjects will complete the Minnesota Nicotine Withdrawal Scale (MNWS), the Subjective State Scale (SSS) and the Questionnaire of Smoking Urges (QSU-Brief). Subjects will also be asked to report any adverse events they have experienced. The Minnesota Nicotine Withdrawal Scale, is a widely used scale to assess nicotine withdrawal symptoms.¹⁵ The positive affect and distress subscales of the SSS, have been found to be reliable at assessing these mood symptoms (alphas are 0.85 and 0.82, respectively).¹⁶ The Brief version of the Questionnaire of Smoking Urges (QSU-Brief) is a commonly used scale to assess nicotine craving with a score for each of two factors (i.e. intention and desire to smoke,

anticipation of relief from negative affect) calculated in order to examine several aspects of the urge to smoke.¹⁷

5 Potential Risks of Study Participation and Protection Against Risk

a. Risks to subjects: Levomilnacipran is generally well tolerated with the most common side effects reported being nausea / vomiting, constipation, excessive sweating, increased heart rate, urinary hesitation, palpitations and erectile dysfunction. Although occurring rarely other side effects including but not limited to mania, rash and allergic reaction, mydriasis, increases in blood pressure and abnormal bleeding have been occasionally reported. There is the possibility that when discontinuing levomilnacipran, subjects may experience a withdrawal syndrome that includes symptoms of dizziness, nausea and paresthesias. Questionnaires will be used to assess a variety of measures to ensure eligibility for the study and to measure outcomes of interest such as cigarette craving and withdrawal symptoms. Some of these questionnaires may ask questions that subjects would consider personal.

As with any medication, there is a risk that unanticipated side effects may occur.

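### Increased heart rate and blood pressure are named as risks of levomilnacipran, but no visit after screening is stated to measure either, so the protocol describes no way of seeing a symptomless rise.

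*Combined protocol and SAP*

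**What the plan says.** Section 5a (Risks to subjects) gives the most common side effects as "nausea / vomiting, constipation, excessive sweating, increased heart rate, urinary hesitation, palpitations and erectile dysfunction". It then turns to effects described as rare and says that "mania, rash and allergic reaction, mydriasis, increases in blood pressure and abnormal bleeding have been occasionally reported".

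The only physical examination is at the screening visit (Section 4, c.1), where "a physical exam will be performed to ensure that subjects are in generally good health". The text does not say whether it includes blood pressure or heart rate.

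The stated assessments after screening are:
- Week 2, two visits (Section 4, c.2): "Adverse events and subjective measures such as craving and withdrawal symptom severity will be assessed at each visit".
- Week 3, five daily visits (Section 4, c.2): "smoking status will be evaluated by measuring exhaled carbon monoxide (CO) concentrations with a value of < 5 ppm confirming abstinence".
- Every visit (Section 4, Outcome Measures): "subjects will complete the Minnesota Nicotine Withdrawal Scale (MNWS), the Subjective State Scale (SSS) and the Questionnaire of Smoking Urges (QSU-Brief"), plus adverse events that the subject reports.

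Section 7 (DSMP) finds adverse effects by asking: "At the conclusion of each visit subjects will be asked whether they have had any side effects". Details and severity are pursued only if the answer is yes. The outcome list in Section 6 a.2 contains no vital sign, and the safety comparison in a.4 is the frequency of adverse events reported by subjects.

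**The concern.** Asking about side effects works for effects that a person notices. A rise in blood pressure can occur without symptoms, and so can some rises in heart rate. For these the plan names the risk but describes no means of observing it.

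Two things are at stake. The first is safety oversight: Section 7 makes the principal investigator and the study physician responsible for monitoring, yet no scheduled assessment would bring them a symptomless change. The second is information. This is a pilot meant to inform larger studies, and each completing subject is seen on both drug and placebo. That design could give a within-subject estimate of the drug's effect on both measures, but as written the adverse-event comparison can reflect only what subjects feel and report.

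**Working it through.** No power or error-rate formula applies. The check has two parts: the visit count, and a comparison of the named risks with the stated assessments.

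**Visit count.** Inputs from Section 4, c.1 and c.2: one screening visit, then in each of two periods 2 baseline-week visits, 2 titration-week visits and 5 quit-week visits.
- Visits per period: 2 + 2 + 5 = 9.
- Total visits: 1 + 2 × 9 = 19, which reproduces the plan's figure.
- Visits while capsules are being taken, per period: 2 + 5 = 7. Each completing subject therefore has 7 visits on levomilnacipran and 7 on placebo. Only the first 7 carry the drug risk; the placebo visits matter as the comparator.
- Dosing days per period: 2 + 10 = 12, consistent with a titration week of 7 days plus 5 quit days.
- With the 52 completers planned in Section 6 a.5, visits on levomilnacipran number 52 × 7 = 364. None has a stated blood pressure or heart rate reading.

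**Risks against assessments.**
- Increased heart rate (common): no reading is stated. Palpitations appear in the same list, so part of this risk can be reported.
- Increased blood pressure (rare): no reading is stated, and no accompanying symptom is named that would bring it to light.
- The only physiological measure stated at the 7 on-drug visits is exhaled carbon monoxide in week 3, which serves to verify abstinence.

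**Whether other protections fill the gap.** Section 5b relies on exclusions, an age limit and a low dose. Exclusions and the age limit reduce risk at entry but do not reveal a change on treatment. The effects named as less likely at this dose are erectile dysfunction, urinary hesitancy and withdrawal symptoms; neither heart rate nor blood pressure is mentioned. The same paragraph concedes that many side effects are not reported to depend on dose.

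**How the discontinuation provisions could be reached.** Section 7 ends participation for a side effect rated above moderate, for symptoms that the investigators judge sufficient, for an important new medical condition, or for starting a problematic medication. A subject's report can set off the first two. The third could be met by a diagnosis made elsewhere. No study measurement is tied to any of them.

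**The case against.** The strongest reply is that the documents do not contradict themselves. Section 5a discloses risks, Section 7 describes adverse-event monitoring, and nothing promises a dedicated measurement for each risk. Mania and abnormal bleeding stand in the same sentence as blood pressure and have no test on treatment either. The subjects are generally healthy adults aged up to 55, exposure is 12 days, the dose is the lowest recommended for depression, and blood pressure increases are called rare. Subjects are asked about side effects at every visit, on five consecutive days in week 3, and by telephone about a week after completion.

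Most of this stands, and it limits the weight of the point. It does not remove it. Bleeding or a change in mood can often be noticed by the subject or by others; a moderate rise in blood pressure may not be. More frequent questions do not help with an effect that the subject cannot perceive.

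A reader might go further in four ways that the documents do not support:
- That a rise cannot be detected at all, or can never lead to discontinuation. Palpitations and symptomatic rises can be reported, and a condition found outside the study can meet the medical-condition provision.
- That all 64 enrolled smokers are exposed. Enrolment allows for 20% attrition, and anyone assigned placebo first who leaves before period 2 never takes the drug.
- That the case for levomilnacipran over nortriptyline is undermined. That case (Sections 1 and 3) concerns muscarinic and histamine effects, makes no blood pressure claim, and the trial has no nortriptyline arm.
- That staff certainly take no readings. Section 4, c.2 says the visit procedures are modelled on published work, which was not available for this review. What can be said is that the protocol states no such reading.

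**Conclusion.** The point holds as a cheap and worthwhile improvement. The plan names one common and one rarer cardiovascular effect and states no measurement of either after screening. A symptomless rise would not be shown by any described procedure at the 7 on-drug visits per completing subject, nor would it appear in the planned safety comparison.

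This rests on two assumptions: that such a rise can occur without symptoms, and that the protocol lists its visit procedures fully. If readings are already taken under the published methods, the measurement change reduces to stating them. No efficacy analysis, power figure or sample size is affected.

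**What to change.** Record seated blood pressure and heart rate at clinic visits that already exist, identically in both periods: at least one baseline-week visit before capsules are dispensed, and visits on capsules in weeks 2 and 3. One workable set is the second baseline visit, both week-2 visits, and the first and last week-3 visits, which makes 5 per period and 10 in all. Week-2 readings come before the planned change in smoking, so they help to separate a drug effect from an effect of abstinence.

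Add to Section 6 a.4 a descriptive summary beside the adverse events. For each subject, take the change from that period's own baseline, on drug minus on placebo; report the mean, standard deviation and confidence interval, and the largest individual rises. List the readings of subjects who leave early, since a paired summary would omit them.

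The sponsor should also reconcile Section 5a with Section 7 by stating how these readings reach the principal investigator and the study physician under the existing monitoring plan. Any clinical threshold or action is for the investigators; none is proposed here.

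The cost is a few extra minutes at the chosen visits, some data entry, physician review and a small added analysis. It requires no new visit and no invasive procedure.
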